**Study Title: Investigation of Potential Therapeutic Effects of Pulsed
Electromagnetic Field for the Treatment of Symptoms Associated with Interstitial
Cystitis/Bladder Pain Syndrome**

IRB00068066

NCT04540887

Study Title: Investigation of Potential Therapeutic Effects of Pulsed Electromagnetic Field for the Treatment of Symptoms Associated with Interstitial Cystitis/Bladder Pain Syndrome

Background, Rationale and Context

Interstitial cystitis/bladder pain syndrome (IC/BPS) is a clinical diagnosis based primarily on chronic symptoms of pain perceived by the patient to emanate from the bladder and/or pelvis associated with urinary urgency or frequency in the absence of another identified cause for the symptoms¹. Although it is not a life-threatening disease, the chronicity and severity of pain, along with urinary symptoms, causes great impairment in a patient's quality of life². IC/BPS poses as a significant clinical challenge for many reasons. For one, the pathophysiology described in the literature is incompletely determined and likely multi-factorial, including factors such as inflammation, neurovascular dysfunction, ion imbalance, and impaired urothelial cell integrity^{3,4,5}. Consequently, there are many options for IC/BPS therapy, many of which are driven primarily by patient-reported symptoms. In this regard, IC/BPS patients with moderate to severe pain typically require multi-modal therapy, often resulting in incomplete or no resolution of symptoms. Another clinical challenge is the heterogeneity of the symptoms. While pelvic pain is the distinguishing characteristic, patients with IC/BPS also routinely present with additional urological and non-urological medical symptoms and syndromes^{6,7}. This has led to the description of two specific sub-phenotypes in IC/BPS based on anesthetized bladder capacity (BC), in which patients with BC < 400 cc are more likely to experience severe pain, urgency and frequency (bladder centric sub-phenotype), and patients with BC > 400 cc (non-bladder centric sub-phenotype) have a higher prevalence of non-urological associated syndromes (NUAS) such as fibromyalgia, chronic fatigue symptoms, irritable bowel syndrome, endometriosis and sicca syndrome^{8,9}.

The current landscape of IC/BPS therapies is vast and imperfect, with the level of invasiveness ranging broadly from lifestyle and behavioral changes to total cystectomy (for refractory end-stage disease). Current non-invasive treatments, including behavioral changes, dietary restrictions, and pelvic floor physical therapy have shown benefits in pain mitigation, but may not demonstrate consistent efficacy in more severe cases¹⁰. Pharmacologic strategies, such as NSAIDs and opiates, have also shown little evidence demonstrating consistent efficacy for treating the chronic pain state, and certainly are not without adverse effect profiles¹¹. More invasive modalities such as cystoscopy with hydrodistention, botulinum toxin injections, or total cystectomies carry morbidity and procedural risk. Furthermore, there is a clear need for a new therapeutic strategy for IC/BPS management, as there is currently no standardized approach that provides relief for all, or even most, patients.

Pulsed Electromagnetic Field (PEMF) therapy may present a promising alternative therapy for IC/BPS. PEMF is a safe, non-invasive, and effective therapy currently used for wound healing,

bone-related diseases (osteoarthritis, RA), and chronic pain states (chronic lower back pain, fibromyalgia), the latter of which is frequently associated with IC/BPS as NUAS. Based on Faraday's law, electromagnetic interactions (e.g. PEMF) with biological processes and conditions (e.g. IC/BPS) will theoretically address many of the proposed pathophysiological causes of the condition. While the mechanism(s) of action are not fully understood, PEMF therapy has been shown in several studies (randomized, double-blinded, placebo-controlled trials) to decrease the output of pro-inflammatory proteins, improve oxygenation of blood and tissue, stabilize transmembrane action potential and ion channels, and stimulate tissue regeneration¹²⁻¹⁵. Thus, PEMF may provide a safe, non-invasive therapeutic option that would be complementary to, or serve as an alternative for, the treatments that are currently being administered in IC/BPS for pain reduction. Of note, PEMF has demonstrated an excellent safety profile with no associated systemic risks reported to date¹⁶. Additionally, the application of exogenous PEMF to stimulate the pelvic floor muscle has recently been introduced for treating urge and/or stress urinary incontinence and overactive bladder¹⁷. Furthermore, if patient safety and efficacy for pain reduction are demonstrated, these feasibility studies will provide the foundation for larger multi-site trials to determine additional parameters regarding the appropriate number of treatments as well as the duration of benefit (pain relief) following treatments.

Objectives

The objective of this pilot study is to test the idea that PEMF therapy will serve as a safe, non-invasive therapeutic modality that can effectively improve the chronic pain and/or associated symptoms of IC/BPS patients. We hypothesize that PEMF therapy will result in significant pain reduction in IC/BPS patients, specifically those with a non-bladder centric phenotype.

Published results from randomized, double-blinded, placebo-controlled clinical trials that have evaluated the efficacy of PEMF for pain management in conditions such as lower back pain, osteoarthritis, rheumatoid arthritis, and fibromyalgia have all reported significant pain reduction following PEMF therapy. Chronic pelvic pain and widespread, non-localized pain (beyond the bladder) are common findings in many IC/BPS patients. The proposed mechanism of action of PEMF therapy (increased microcirculation and tissue regenerative capacity through modulation of inflammatory processes) provides a compelling rationale for evaluating the efficacy of PEMF in IC/BPS patient pain relief.

Methods and Measures

Design

This is a single center clinical series evaluating symptom relief following a 4-week trial of PEMF therapy. From our registry of IC/BPS patients we will recruit women, ages 18-80, who

have met all inclusion and exclusion criteria, which includes demonstration of an anesthetic BC > 400 cc (non-bladder-centric phenotype) and a current numeric rating scale (NRS) pain score for pelvic pain ≥ 6 . Upon enrollment, each patient will be taught how to administer home treatment with the BEMER (Bio Electro Magnetic Energy Regulation) PEMF devices which consist of a total body mat (B.Body) plus a targeted pelvic mat (B.Pad). Following the brief in-clinic training, participants will be sent home with the PEMF devices (pre-set to deliver the same level of energy each time) and will self-administer 8 minute PEMF therapy sessions, twice daily (once in the morning, once in the evening).

Patient assessments will occur at three time points: (1) enrollment, (2) after four weeks of treatment, and (3) at twelve weeks post-enrollment. The primary outcome measure will be the change in NRS pain score for pelvic pain. A decrease of at least 2 points on the NRS pain scale will be considered as representative of a significant decrease in pelvic (and/or widespread) pain. Secondary outcomes will be assessed by validated IC/BPS questionnaires (O'Leary-Sant indices), voiding characteristics (patient recorded voiding diary), change in perceived pain as determined by pain body maps, and the patient's overall impression of change (Global Response Assessment). Follow-up assessments will be completed remotely through phone or email surveys. During the twelve-week study, patients will not undergo any of the following IC/BPS therapies: cystoscopy with hydrodistention, bladder instillations, or trigger point injections. Patients that were prescribed a stable dose of pro re nata (PRN) narcotic medication at least three months prior to enrollment will be included in the study. Patients will be expected to report which, if any, pain medications they have been taking prior to enrollment and what additional medications they plan to use throughout the duration of the study. The following IC/BPS oral medications will be allowed during this time: amitriptyline, cimetidine, hydroxyzine, and pentosan polysulfate.

The demographic data will be extracted from patient's electronic medical record. The basic office evaluation will be composed of detailed medical history, physical exam, urinalysis, urine culture, 7-days voiding diary, O'Leary-Sant symptom and problem index (ICPI/ICSI), Pelvic Pain and Urgency/Frequency Patient Symptom (PUF) scale, Genitourinary Pain Index (GUPI), SF-36 quality of life questionnaires, and numeric rating scale for pain in the last 24 hours.

In this proof of concept study, *all* participants will receive the full therapy (i.e. there will not be a control group). In the double-blind placebo-controlled crossover trial that will follow this proof-of-concept study, we will have access to placebo (sham) mats for use as a control.

Subject Selection Criteria

Participants will be recruited from the Urology Clinic at Wake Forest Baptist Hospital and all study participants will provide written informed consent.

- **Inclusion Criteria**

Female patients between 18 to 80 years with a previously established clinical diagnosis of IC/BPS. Participants must have an anesthetic BC > 400 cc, a current NRS score ≥ 6 , and have no cognitive deficits. Patients will be required to attest that they will not receive a new prescription and/or an increased dose of narcotic medication while participating in the study.

- **Exclusion Criteria**

Any history of bladder, uterine, ovarian, or vaginal cancer, urethral diverticulum, spinal cord injury, stroke, Parkinson's disease, multiple sclerosis, spina bifida, radiation cystitis, cyclophosphamide treatment, immunosuppressive therapy in consequence of transplantation, allogeneic cellular transplantation, or bone marrow or stem cell transplantations, deep vein thrombosis, or genital herpes. Patients will be excluded from this study if they have an implanted pace-maker, metal prosthesis, urinary tract infection, BMI > 40, or are currently pregnant.

- **Sample Size**

For this small pilot study, we will enroll up to 10 study patients with the goal of achieving a full dataset from at least 6 patients.

Human Subjects Protection

Informed Consent: An IRB-approved written informed consent will be obtained from each subject. Patients will initially be contacted and introduced to the study via phone call from a study team member to discuss study details and answer questions. If they agree, an electronic copy of the IRB-approved consent form will be e-mailed to the patient. Informed consent and signature will be acquired in the Wake Forest University Urology Outpatient Clinic prior to training on the PEMF device.

Confidentiality and Privacy: Confidentiality will be protected by collecting only information needed to accomplish future demographic matching (i.e. patient's age, ethnicity, BMI, etc.), minimizing to the fullest extent possible the collection of any information that could directly identify subjects, and maintaining all study information in a secure manner. To help ensure subject privacy and confidentiality, a unique study identifier will appear on the data collection form. Any collected patient identifying information corresponding to the unique study identifier will be maintained on a separate master log. The master log will be kept secure, with access limited to designated study personnel. Following data collection, subject identifying information will be destroyed at the earliest opportunity consistent with data validation and study design,

producing an anonymous analytical data set. Data and records will be kept locked and secured, with access limited to study staff and password protection on all data stored electronically. No reference to any individual participant will appear in reports, presentations, or publications that may arise from this study.

Every effort will be made to maintain participant privacy. Data will only be released to scientists who are qualified and prepared to conduct a research study. If publications or presentations result from this research, participants will not be identified by name or any other personal identifier.

Data and Safety Monitoring

The principal investigator and study coordinator will be responsible for the overall monitoring of the data and safety of study participants and will ensure that the subjects' information is not revealed. The principal investigator will be assisted by other members of the study staff.

Reporting of Unanticipated Problems, Adverse Events or Deviations

Any unanticipated problems, serious and unexpected adverse events, deviations, or protocol changes will be promptly reported by the principal investigator or designated member of the research team to the IRB and sponsor or appropriate government agency if appropriate.

References

1. Van de Merwe JP NJ, Bouchelouche P, Bouchelouche K, Cervigni M, Daha LK, Elneil S, Fall M, Hohlbrugger G, Irwin P, Mortensen S, van Ophoven A, Osborne JL, Peeker R, Richter B, Riedl C, Sairanen J, Tinzi M, Wyndaele JJ. Diagnostic criteria, classification, and nomenclature for painful bladder syndrome/interstitial cystitis: an ESSIC proposal. *Eur Urol*. 2008;53(1):60-67.
4. Parsons CL. "The role of leaky epithelium and potassium in the generation of bladder symptoms in interstitial cystitis/overactive bladder, urethral syndrome, prostatitis and gynaecological chronic pelvic pain." *BJUI*. 2010 (107): 370-375.

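### The plan does not separate the NRS score that qualifies a patient (6 or more) from the baseline of the primary change; if one reading serves both, regression to the mean inflates the uncontrolled fall in pain

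*Combined protocol and SAP*

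**What the plan says.** The Design section requires "a current numeric rating scale (NRS) pain score for pelvic pain ≥ 6" for entry. The Inclusion Criteria repeat the cut-off, without the word pelvic and without a visit, date or recall period.

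The outcome is on the same scale: "The primary outcome measure will be the change in NRS pain score for pelvic pain". The timing is "Patient assessments will occur at three time points: (1) enrollment, (2) after four weeks of treatment, and (3) at twelve weeks post-enrollment", so only the first assessment precedes treatment. Device training comes at the same point: "Upon enrollment, each patient will be taught how to administer home treatment". The response mark is also given: "A decrease of at least 2 points on the NRS pain scale will be considered as representative of a significant decrease".

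The office evaluation includes a "numeric rating scale for pain in the last 24 hours". It is not described as pelvic and is tied neither to eligibility nor to the primary change. No screening NRS, run-in, repeat reading or averaging is described, and regression to the mean is not mentioned.

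The plan is open about being uncontrolled ("there will not be a control group") and announces a "double-blind placebo-controlled crossover trial that will follow this proof-of-concept study".

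**The concern.** An NRS score is a patient's usual level plus day-to-day variation. Choosing patients because a reading is at or above 6 favours those whose variation happened to be upward that day. If that reading is also the starting point of the change, the later score is expected to be lower even when treatment does nothing. This holds whenever the test-retest correlation is below 1 and the selected group scores above the average of the population it came from. A control group selected in the same way would cancel the effect, but this design has none.

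The Objectives hypothesize significant pain reduction, and the end of the Background makes larger multi-site trials depend on efficacy for pain reduction being shown. The change score, and the number of patients reaching a 2-point fall, are part of that evidence. Placebo response and natural course cannot be separated from treatment in one arm, but the selection artefact can at least be reduced at the design stage.

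**Working it through.** **The plan's own figure.** The Sample Size section gives up to 10 enrolled and at least 6 with a full dataset. It states no SD, effect, error rate or power, so there is no calculation to reproduce.

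**Inputs from the protocol.** Cut-off 6 or more; response mark a fall of 2 or more; single arm; n = 6 to 10; first post-treatment reading at 4 weeks.

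**Inputs assumed.** Registry NRS mean 4 to 7, SD 1.5 to 2.5, test-retest correlation r 0.5 to 0.9. The case mean 5, SD 2, r 0.7 is used as an illustration. The treatment effect is set to zero throughout.

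**Step 1: formula.** For a roughly normal score, the expected spurious fall is (1 − r) × (E[X | X ≥ 6] − mean). The cut-off lies (6 − 5)/2 = 0.5 SD above the mean. The mean of a standard normal above 0.5 is 1.141, so E[X | X ≥ 6] = 5 + 2 × 1.141 = 7.28. The fall is 0.3 × 2.28 = 0.68 points.

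**Step 2: simulation on the integer 0–10 scale.** Variance r × SD² was stable and (1 − r) × SD² was noise. Patients were kept if the qualifying score was 6 or more.

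| Illustrative case, no treatment effect | Qualifying reading is the baseline | Independent separate baseline |
|---|---|---|
| Mean baseline | 6.96 | 6.34 |
| Mean at week 4 | 6.34 | 6.34 |
| Mean fall | 0.62 | 0.00 |
| SD of change | 1.49 | 1.59 |
| Fall of 2 or more | 27% | 17% |
| Chance of at least 3 of 6 such patients | 0.21 | 0.06 |

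The fall of 0.62 is 0.62/2 = 31% of the 2-point mark. The extra share reaching it is about 10 percentage points, or 1 patient in 10.

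**Step 3: range.** The smallest fall is 0.06 points (mean 7, SD 1.5, r 0.9) and the largest about 1.55 (mean 4, SD 2.5, r 0.5). The added share falling by 2 or more runs from 0.3 to about 26 percentage points. In no case does the artefact alone give a mean fall of 2.

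**Step 4: sampling noise.** With a shared reading, the standard error of the mean change is 1.49/√6 = 0.61 or 1.49/√10 = 0.47, about the size of the illustrative bias.

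**Step 5: how much a separate reading removes.** An independent second reading removes all of the artefact, but readings close in time share noise. Daily noise correlations of 0.8 and 0.9 were assumed, with week 4 falling 28 days after baseline. The shared-reading fall is then 0.62 and 0.59.

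| Gap between readings | Residual fall, 0.8 | Residual fall, 0.9 | Share of artefact left |
|---|---|---|---|
| 1 day | 0.46 | 0.50 | 75% to 85% |
| 7 days | 0.12 | 0.25 | 20% to 43% |
| 14 days | 0.03 | 0.12 | 5% to 20% |

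**Step 6: re-applying the cut-off.** If an independent second reading must also be 6 or more, 0.41 of the 0.62 points remain.

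**The case against.** The strongest reply is that no fault is shown, only a silence. The protocol recruits from a registry women who already meet the criteria, telephones them before the clinic visit, and then lists enrollment as an assessment. It also asks for a current score in one place and a 24-hour score in another. Two readings are consistent with this. That is fair, and it is why the point is conditional. But no NRS is said to be taken by telephone, the 7-day diary is a voiding diary, and the baseline of a primary change score is left undefined on either reading.

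Second, the size is wholly assumed and spans roughly 25-fold. At mean 6, SD 2, r 0.8 the fall is only 0.29 points, and the share falling by 2 or more is 16% against 12%. This stands: the documents cannot say whether the artefact is trivial or material, only which way it points.

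Third, it decides little. No test or success count hangs on the change, noise is as large as the bias, placebo response remains, and a sham-controlled trial is planned. This also stands and keeps the point at the level of a suggested improvement. Disclosing that there is no control group does not, however, disclose this particular bias.

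Fourth, the remedy is partial: a gap of one day achieves little, and the protocol gives no interval between the telephone call and the visit. That is correct, so the gap matters and a disclosure-only fallback is reasonable.

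**Conclusion.** The concern holds as stated. The plan does not say that the qualifying score and the baseline are different readings. If they are the same, the primary change is biased toward benefit. The direction follows from the selection rule. The size rests on assumed registry values: about 0.6 points in the illustrative case, 0.1 to 1.6 over the range tried, with from under 1 to about 26 percentage points more patients falling by 2 or more. Given the pilot aim, 6 to 10 patients and the planned sham-controlled trial, this is worth considering and does not undermine the study. Confidence is medium, because the text does not settle whether one reading is used and gives no NRS data.

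**What to change.** Keep 6 or more for eligibility, and reword current in the inclusion criterion so that it names the screening reading. Then:

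- Define the baseline of the primary change as a separate pelvic-pain NRS, taken before the first session and not used for eligibility, with the same wording and recall period as at week 4.
- State whether the 24-hour NRS in the office evaluation is that item.
- Take the two readings as far apart as existing contacts allow, for example at the pre-visit contact and the clinic visit, subject to IRB agreement on asking before signed consent.
- State that the cut-off is not re-applied at baseline, since that would restore much of the bias.

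If a separate reading is not feasible, say that the qualifying score is the baseline, report the change as uncontrolled, and name regression to the mean as one explanation. That costs a sentence or two.

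The full change costs one extra question, possible IRB agreement, a reworded criterion and perhaps a later clinic visit. In the illustrative case with a gap of 7 to 14 days, the mean baseline would be about 6.4 to 6.6 instead of 7.0. About 22% to 30% of patients (2 or 3 of 10) would read below 6 at baseline and stay in. The observed change would be smaller. Its standard error would be slightly larger: 0.48 to 0.50 instead of 0.47 at n = 10, and up to 0.65 instead of 0.61 at n = 6. Placebo response and natural course would remain unseparated.

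### The enrollment pain score appears to be taken in the clinic and both follow-up scores by phone or email, so any mode difference is confounded with the primary before-after change.

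*Combined protocol and SAP*

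**What the plan says.** All of this is in the combined protocol and SAP, in the Design section of Methods and Measures unless stated otherwise.

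- Endpoint: "The primary outcome measure will be the change in NRS pain score for pelvic pain". A fall of at least 2 points counts as a significant decrease.
- Timing: "Patient assessments will occur at three time points: (1) enrollment, (2) after four weeks of treatment, and (3) at twelve weeks post-enrollment".
- Enrollment measures: "The basic office evaluation will be composed of detailed medical history, physical exam, urinalysis, urine culture", followed by a 7-day voiding diary and several questionnaires, and ending with "SF-36 quality of life questionnaires, and numeric rating scale for pain in the last 24 hours".
- Setting at enrollment: Human Subjects Protection states "Informed consent and signature will be acquired in the Wake Forest University Urology Outpatient Clinic prior to training on the PEMF device".
- Follow-up: "Follow-up assessments will be completed remotely through phone or email surveys".
- Secondary outcomes include "voiding characteristics (patient recorded voiding diary), change in perceived pain as determined by pain body maps".
- Control: every participant is treated and there is no comparison group. A sham-controlled crossover trial is to follow.
- Size (Sample Size): up to 10 enrolled, with full data wanted from at least 6.

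The plan does not call for a remote baseline, a single follow-up mode per patient or per visit, a record of the mode used, or any analysis or caveat about mode.

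**The concern.** A pain score can depend on how it is asked for: spoken to staff or written alone, in a clinic or at home. In a trial with a concurrent control, a shift common to both arms largely cancels in the comparison. Here there is nothing for it to cancel against. On the most natural reading, the mode changes exactly where treatment begins, with the clinic before and remote contact after. Leaving phone or email open adds a second uncontrolled difference, between patients and between weeks 4 and 12.

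The question wording is also loose. Eligibility uses a current pelvic-pain score, the office item is a "numeric rating scale for pain in the last 24 hours" with no body site named, and the follow-up item's recall period is not given.

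At stake is the primary estimate of a pilot that, by its own account, is meant to support larger multi-site trials. With as few as 6 complete datasets, adjusting for mode afterwards is not realistic.

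**Working it through.** **1. Can a plan figure be reproduced?** No. The sample size is given without alpha, power, SD or expected effect. The point rests on design logic, and the figures below are illustrations.

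**2. Structure.** For one patient, let d be the true improvement and m the mode shift, defined as clinic score minus remote score for the same pain. A positive m means that remote scores run lower.

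Expected observed fall = d + m (+ placebo response and regression to the mean)

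The plan has no control arm, no same-mode baseline and no comparison of modes, so d and m cannot be separated.

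**3. Illustration with selection on a high entry score.**

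From the plan: entry NRS of at least 6, and the 2-point rule.

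Assumed: true pain normal with mean 6 and between-patient SD 2; within-patient (occasion) SD 1.5; scores rounded to integers 0 to 10; d = 0; m between -1.0 and +1.0.

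Method: simulate 4,000,000 patients. Baseline = true + error; keep those with baseline of at least 6; follow-up = true + new error - m; count falls of at least 2. The last two columns multiply the share by 6 and by 10.

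| Shift m | Share with a 2-point fall | Of 6 patients | Of 10 patients |
|---|---|---|---|
| -1.0 (remote higher) | 16% | 1.0 | 1.6 |
| -0.5 | 23% | 1.4 | 2.3 |
| 0 | 31% | 1.9 | 3.1 |
| +0.5 (remote lower) | 41% | 2.4 | 4.1 |
| +1.0 | 51% | 3.0 | 5.1 |

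The 31% at m = 0 has nothing to do with mode. It comes from measurement noise together with selection on a high entry score. Only the differences from 31% illustrate the shift. Against the 2-point rule, shifts of 0.5 and 1.0 are 0.5/2 = 25% and 1.0/2 = 50%.

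**4. Cross-check with a simpler model.** Assume no selection and a normally distributed change with d = 0:

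P(fall of at least 2) = 1 - Φ((2 - m)/SD of change)

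With SD 2.0:

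- m = 0: 1 - Φ(1.00) = 16%
- m = +0.5: 1 - Φ(0.75) = 23%
- m = +1.0: 1 - Φ(0.50) = 31%
- m = -0.5: 1 - Φ(1.25) = 11%
- m = -1.0: 1 - Φ(1.50) = 7%

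For SD of change 1.5 and 2.5, the share at m = 0 is 9% and 21%, and at m = +1.0 it is 25% and 35%. The levels differ from step 3 because there is no selection, but the share moves in the same way in both directions.

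**5. With one common form.** To the extent that the shift comes from the form or from who asks, m goes to 0 and the shares return to the m = 0 values: 31% in step 3 and 16% in step 4 at SD 2.0. They do not go to zero.

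**The case against.** The strongest reply has five parts.

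- **The clinic baseline is inferred.** No sentence says that the score used for the change is taken in the clinic. The mode of the eligibility score is not given, and first contact is by phone. This stands as a caveat. But the office evaluation, together with in-clinic consent and training, makes the clinic much the likeliest reading. If the baseline mode is in fact open, the plan still has to fix it.
- **The direction is unknown.** A reader might infer a bias toward benefit, because patients know they are treated and may please the caller. The documents do not say who makes the calls, or whether the enrollment score is spoken or written. If it is spoken to clinic staff and follow-up is a form completed alone, the same argument points the other way. This stands in full, so both directions are shown.
- **Other assumptions matter as much.** Varying the population mean from 5 to 7 and the within-patient SD from 1 to 2 moves the zero-shift share from about 16% to 46%. A 0.5-point downward shift adds only about 0.6 responders among 6 patients or 0.9 among 10. This stands: confounding shows that the bias cannot be identified, not that it is large.
- **Diary and body map.** A reader might infer that phone follow-up makes these outcomes unobtainable. The documents do not support that: diary entries can be read out and a map can be emailed. What is missing is a stated route for returning them.
- **It is an open pilot.** The plan says plainly that it has no control and that a sham-controlled trial will follow. Placebo response and regression to the mean are confounded in the same way and may well be larger. That lowers the priority but does not remove the point, because those limits come with the chosen design and a change of mode does not.

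**Conclusion.** The concern holds in a limited form. As written, the plan appears to change the mode of the primary measurement between baseline and follow-up and leaves the follow-up mode open. With no control arm, any resulting shift is inseparable from the treatment effect. This rests on reading the enrollment NRS as an in-clinic score, which is a strong inference and not an explicit statement.

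Neither the size nor the direction of a shift is in the documents. Under the assumptions of step 3, shifts of up to 1 point either way move the share of apparent responders from 31% to anywhere between 16% and 51% with no treatment effect at all. A reader might take this as evidence that the trial is biased toward benefit, or treat the whole 51% as a mode effect. Neither is supported: the shifts are assumed, benefit could equally be hidden, and the 31% arises without any shift.

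It is worth correcting before enrollment because the remedy is cheap, but it is secondary to the limits that any uncontrolled series carries.

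**What to change.** - Collect the pelvic-pain NRS and the questionnaires at enrollment, week 4 and week 12 with one identical self-completed form: same item, same body site, same recall period.
- At enrollment, have the patient complete it without staff asking, after consent and before device training, preferably through the same remote survey link used later.
- Use the phone for reminders only.
- Send the body map and the voiding diary as forms to be returned, and state how they are returned.
- Record the mode of every score, including any taken on paper or by phone, and repeat the primary summary using only scores from the standard form.

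Cost: one electronic form, which email follow-up already requires, and some protocol wording. A few patients without email will need a paper copy, which is itself another mode and so must be recorded. Treatment, eligibility and sample size do not change.

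Limits: the form is equalised but the setting may not be, if the enrollment form is completed in the clinic. Placebo response and regression to the mean remain and should be named as limits when the results are reported.
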